## **10.0 STATISTICAL CONSIDERATIONS**

### **10.1 Study Design**

This is a Phase Ib study evaluating the safety and efficacy of pembrolizumab combined with pralatrexate (Arm A) or decitabine (Arm C) or decitabine and pralatrexate (Arm B) in patients with peripheral T-cell lymphoma (PTCL) and cutaneous T-cell lymphoma (CTCL). In all arms, toxicity will be assessed according to the NCI Common Toxicity Criteria for Adverse Events (CTCAE), version 5.0. Dose-limiting toxicity (DLT) is a binary outcome (yes/no) and will be determined by adverse events occurring during the first cycle of treatment (see Section 5.3 for DLT definition). In all arms, the maximum tolerated dose (MTD) is defined as the dose combination with a DLT rate closest to the target DLT rate of 25%. The study will accrue participants in cohorts of size 1 in all arms. After accrual of a participant to an arm, the accumulating DLT data will be used to update the model-based estimated DLT

probabilities for each dose level. These estimates will then be used to update the recommended dose level for the next participant accrued to that arm of the study.

Arms A and C:

The primary objectives of Arms A and C is to determine the MTD, defined by acceptable toxicity, of decitabine (Arm C) or pralatrexate (Arm A) (plus a fixed dose of pembrolizumab) from among the 3 study dose levels in the following tables, and to evaluate efficacy, as determined by overall response rate, at the estimated MTD.

Arm A		
Dose Level	Pralatrexate	Pembrolizumab*
Level 1 (start)	30 mg/m  day 1, 8, 15	200 mg day 1
Level -1	30 mg/m  day 1, 15	200 mg day 1
Level -2	20 mg/m  day 1, 15	200 mg day 1

Arm C		
Dose Level	Decitabine	Pembrolizumab*
Level 1 (start)	20 mg/m  day 1->5	200 mg day 8
Level -1	20 mg/m  day 1->3	200 mg day 8
Level -2	10 mg/m  day 1->3	200 mg day 8

Based on the accumulated data from the previous 5 subjects (1 observed DLT) accrued to Arm A, the first eligible subject in Arm A will be entered onto Level 1. Based upon the accumulated data from the previous 4 subjects (2 observed DLTs) accrued to Arm C, the first eligible subject in Arm C will be entered onto Level -1.

Arm B:

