## 10.2 Dose allocation

### Arms A and C

Dose allocation in Arms A and C will be based upon a continual reassessment method (CRM), which uses a model for the probability of DLT and the accumulated DLT data at each dose level to sequentially allocate each new patient cohort. Toxicity assessment is based on the occurrence of DLTs, and the minimum follow-up for determination of escalation is one cycle of treatment. The DLT probabilities are modeled using a one-parameter working model  $R(d_i) = \Pr(\text{DLT at dose level } i) \approx \alpha_i^{\exp(a)}$ , where  $\alpha_i$  is the skeleton of the working model. The skeleton values are pre-specified constants and were chosen according to the algorithm of Lee and Cheung, which yields a working model that results in well-performing operating characteristics in a broad range of scenarios. For this study, the skeleton values are  $\alpha_i = (0.08, 0.15, 0.25)$ . Based on the available DLT data  $D = \{(y_i, n_i); i = 1, \dots, 3\}$ , where where  $y_i$  is the number of DLT's and  $n_i$  is the number of subjects treated on study dose level  $i$ , the likelihood is given by  $L(a) \propto \prod_{i=1}^3 (\alpha_i^{\exp(a)})^{y_i} (1 - \alpha_i^{\exp(a)})^{n_i - y_i}$ .

After accrual of each patient into the trial, the DLT probability estimates,  $\tilde{R}(d_i)$ , are updated via  $\tilde{R}(d_i) = \alpha_i^{\exp(\tilde{a})}; \quad \tilde{a} = \arg \max L(a)$ .

These estimates are used to sequentially allocate patients to the dose indicated by the modeling to have the estimated DLT rate closest to 25%. The study will accrue participants in cohorts of size 1 and dose levels will not be skipped. The coherence principle will be used, where the next patient will not be treated at a dose level higher than the current dose level if the current patient experiences a DLT. Additionally, the next patient will not be treated at a dose level lower than the current dose level if the current patient does not experience a DLT. The study will sequentially repeat the estimation procedure after the enrollment and follow-up of each cohort. The allocation procedure will be repeated until sufficient information about the MTD has been obtained according to the stopping rules described below.

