## 10.5 Operating characteristics

### Arms A and C

Simulations were run to display the performance of the design characteristics in Arms A and C using the R statistical programming language. For each scenario, 5000 simulated trials were run using a random seed of 322348. The confidence level used to define the safety stopping guidelines was 80%. Each table reports the true DLT probability at each dose level, the percentage of trials in which each dose level was recommended as the MTD, the average number of participants treated at each dose level, and the percentage of trials stopped early for safety. The results displayed in the following tables were based upon a maximum target accrual of 10 subjects.

Operating characteristics in Arm A for the continual reassessment method with cohorts of size 1. Bold font indicates the level that is the MTD corresponding to a target DLT rate of 25%. Previously, there were 5 participants accrued (1 observed DLT) on dose level 3. Sample size for each scenario is n=10 total (previous plus additional) participants.					
Scenario		Dose level 1	Dose level 2	Dose Level 3	% stopped for safety
1	True DLT prob:	0.05	0.15	0.25	0.0
	MTD selection %	5.7	22.6	71.7	
	Avg # of patients	0.1	0.6	9.3	
2	True DLT prob:	0.15	0.25	0.40	0.24
	MTD selection %	18.9	36.2	44.7	
	Avg # of patients	0.3	1.0	8.7	
3	True DLT prob:	0.25	0.40	0.55	1.24
	MTD selection %	41.2	34.0	23.5	
	Avg # of patients	0.6	1.4	8.0	

Operating characteristics in Arm C for the continual reassessment method with cohorts of size 1. Bold font indicates the level that is the MTD corresponding to a target DLT rate of 25%. Previously, there were 4 participants accrued (1 observed DLT) on dose level 3. Sample size for each scenario is n=10 total (previous plus additional) participants.					
Scenario		Dose level 1	Dose level 2	Dose Level 3	% stopped for safety
1	True DLT prob:	0.05	0.15	0.25	0.0
	MTD selection %	6.9	3.1	62.1	
	Avg # of patients	0.3	1.2	8.5	
2	True DLT prob:	0.15	0.25	0.40	0.52
	MTD selection %	23.6	43.7	32.2	
	Avg # of patients	0.7	1.8	7.5	
3	True DLT prob:	0.25	0.40	0.55	2.24
	MTD selection %	50.1	35.4	12.2	

	Avg # of patients	1.5	2.0	6.5	
--	-------------------	-----	-----	-----	--

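### Arm C scenario 1 selection percentages total 72.1%: the dose level 2 entry of 3.1 should be about 31, and the table's inputs need reconciling before it is re-issued

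*Protocol*

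**What the plan says.** Section 10.5 of the protocol describes simulations for Arms A and C in which "5000 simulated trials were run using a random seed of 322348". For each scenario the tables report "the percentage of trials in which each dose level was recommended as the MTD", the average number treated at each level, and the percentage stopped early for safety, all with a maximum of 10 participants.

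For Arm C scenario 1 the true DLT rates and the safety-stop percentage are printed as "True DLT prob: 0.05 0.15 0.25 0.0". The selection row is "MTD selection % 6.9 3.1 62.1". The caption of the Arm C table gives the data carried into the simulation: "Previously, there were 4 participants accrued (1 observed DLT) on dose level 3". The tables number the levels upward, so their dose level 3 is Level 1 of section 10.1, dose level 2 is Level -1 and dose level 1 is Level -2.

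Section 10.1 bases the next Arm C assignment on the "previous 4 subjects (2 observed DLTs) accrued to Arm C" and places that subject on Level -1. Section 10.2 fixes the skeleton at "0.08, 0.15, 0.25" and allocates to "the dose indicated by the modeling to have the estimated DLT rate closest to 25" per cent. Section 10.3 ends an arm when the recommended level already has 7 participants, and otherwise at 10 participants.

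**The concern.** Selection of one of three levels and a safety stop are the only possible endings of a simulated Arm C trial, and they exclude one another. A row that totals 72.1% leaves 27.9% of trials, about 1,395 of 5,000, without an outcome.

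Finding the MTD is a primary objective of the arm, and this table is the protocol's evidence on how reliably the design does so. Scenario 1 is the only Arm C scenario in which the top level is the true MTD. The printed row makes settling one level too low look rare, at about 3%, when the simulation behind it implies nearly one trial in three.

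**Working it through.** **Step 1: row totals** (three selection percentages plus percentage stopped, all from section 10.5)

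| Row | Sum | Total |
|---|---|---|
| Arm A, scenario 1 | 5.7 + 22.6 + 71.7 + 0.0 | 100.0 |
| Arm A, scenario 2 | 18.9 + 36.2 + 44.7 + 0.24 | 100.04 |
| Arm A, scenario 3 | 41.2 + 34.0 + 23.5 + 1.24 | 99.94 |
| Arm C, scenario 1 | 6.9 + 3.1 + 62.1 + 0.0 | **72.1** |
| Arm C, scenario 2 | 23.6 + 43.7 + 32.2 + 0.52 | 100.02 |
| Arm C, scenario 3 | 50.1 + 35.4 + 12.2 + 2.24 | 99.94 |

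Only Arm C scenario 1 fails, by 27.9 points.

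**Step 2: which cell is wrong.** All DLT paths were enumerated exactly, without Monte Carlo error. Inputs: the power model fitted by maximum likelihood, skeleton 0.08, 0.15, 0.25 and target 25% (section 10.2); 1 DLT in 4 on dose level 3 and a run to 10 participants (section 10.5); safety bounds from section 10.3.

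The method was first tried on a row that closes. For Arm A scenario 1 it gives 5.3 / 22.5 / 72.2, against 5.7 / 22.6 / 71.7 printed.

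For Arm C scenario 1:

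| | Dose level 1 | Dose level 2 | Dose level 3 | Stopped |
|---|---|---|---|---|
| Selection %, printed | 6.9 | 3.1 | 62.1 | 0.0 |
| Selection %, exact | 6.8 | 30.3 | 62.8 | 0.08 |
| Average patients, printed | 0.3 | 1.2 | 8.5 | |
| Average patients, exact | 0.28 | 1.20 | 8.51 | |

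The two outer selection figures and all three patient averages agree, which isolates the dose level 2 entry. Turning the coherence and no-skipping rules on or off does not change these values.

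**Step 3: size.** By subtraction the entry is 100 - 6.9 - 62.1 - 0.0 = 31.0%. The Monte Carlo standard error at that value is sqrt(0.31 × 0.69 / 5000) = 0.65 points. The printed 3.1 is more than 40 standard errors away, while 31.0 is about one from the exact 30.3.

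- Dose level 2 alone: 31.0 / 3.1 = 10-fold.
- Any level below the MTD: 6.9 + 3.1 = 10.0% printed; 6.9 + 31.0 = 37.9% corrected; ratio 3.8.

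**Step 4: do the table's inputs match the rest of the protocol?**

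- *Previous DLTs.* With 1 in 4 on dose level 3, the fitted rate there is 0.25, so exp(a) = 1, the estimates equal the skeleton, and the next subject stays on dose level 3. With 2 in 4, exp(a) = ln 0.5 / ln 0.25 = 0.5. The estimates are then sqrt(0.08) = 0.28, sqrt(0.15) = 0.39 and 0.50. Dose level 1 is closest to 25%, and the rule against skipping levels gives dose level 2. That is Level -1, the assignment in section 10.1. So section 10.1 is consistent with itself and inconsistent with the caption in section 10.5.
- *Scenario 1 from 2 DLTs in 4*, with coherence and no skipping: 12.8 / 57.5 / 29.4, with 0.3% stopped.
- *Scenario 1 from 1 DLT in 4, with the stop at 7 applied:* 4.5 / 18.5 / 76.8. The printed figures match the run without that stop.

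**Limit of the reproduction.** The printed safety-stop percentages are lower than the section 10.3 bounds give; in Arm C scenario 3 they are 2.24 printed and about 7.5 exact. In scenario 1 stops are so rare (0.08%) that this cannot affect the result.

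**The case against.** The strongest reply is that this is an isolated misprint, probably a slipped decimal point, with little effect. Much of that stands. The row prints correct selection as 62.1% with no safety stops, which already implies 37.9% incorrect selection, and anyone who adds the row sees the fault. No allocation rule, stopping bound or sample size in sections 10.2 to 10.4 uses the 3.1. Sections 5.1 and 7.6 open Arm B only after Arms A and C have finished enrolling, and section 10.1 reports 4 subjects already in Arm B. Arm C accrual may therefore be over, although sections 10.1 and 10.4 still describe further Arm C participants. A fault in the PDF text cannot be wholly excluded, but no other row shows one.

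Two stronger readings are tempting. A reader might infer that selection of too-low levels as a whole is understated tenfold. It is not: dose level 1 is also below the MTD in this scenario, so the combined figure is understated 3.8-fold, and tenfold applies to one cell. A reader might also infer that the design's accuracy at the true MTD is misstated. On the caption's inputs it is not, because 62.1% agrees with the exact 62.8%.

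The reply does not rescue the row, which cannot total 72.1% under any inputs. It also shows that changing one digit would only make the row add up under a setting that conflicts with sections 10.1 and 10.3.

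**Conclusion.** The dose level 2 entry for Arm C scenario 1 is wrong as printed and should be about 31%. The failure of the row total needs no assumption beyond the table's own description. Locating the error in the middle cell rests on the caption's setting: 1 DLT in 4, run to 10 participants, without the stop at 7.

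This is a reporting error in the stated performance for a primary objective. It does not show a fault in the dose-finding rules or a risk to participants. Nor should 31.0, or the 62.1 beside it, be read as the performance of Arm C as the protocol now describes it. From the 2 DLTs in 4 of section 10.1, correct selection in this scenario is about 29%. The documents do not settle which count is right. The summary of changes to 11/23/2020 records a correction of the Arm C DLT count in section 10.1 but only reformatting of the tables in section 10.5, which suggests, without proving, that the caption was left behind.

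**What to change.** 1. Correct the dose level 2 entry from the stored simulation output; 31.0 is expected if the decimal point slipped.
2. Reconcile the previous Arm C DLT count between section 10.1 and the section 10.5 caption.
3. State whether the simulations apply the stop at 7 participants in section 10.3, and make the two sections agree.
4. Re-run all three Arm C scenarios with the reconciled inputs and re-issue the table.
5. Before release, check that selection plus safety stops totals 100% in every row.

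The first item costs one number. The rest costs a re-run of existing code and a revised table, with no change to allocation rules, bounds or sample size. The stated performance may look less favourable.

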### 10.3 Stopping rules and MTD definition

#### Arms A and C

Accrual to Arms A and C will be halted and trigger a review by the study investigators and the DSMC to determine if the study should be modified, or permanently closed to further accrual according to the following:

1. Stop the study for safety if the observed DLT rate at the lowest study dose level (Level -2)  $\geq$  the following number of DLTs out of the following number of patients treated at the lowest study dose level. These stopping guidelines are based on whether the lower limit of an Agresti-Coull binomial confidence interval (with 80% confidence) for the lowest study dose level exceeds the target DLT rate. The following bounds were generated using the web application at <http://uvatrapps.uvadcos.io/crmb/>. Note that, given the accrual of previous participants to dose level 1 in Arms A and C, at most 4 participants can be accrued to Level -2 before the maximum sample size is reached.

Stopping guidelines for DLTs at the lowest dose level	
Number of participants	Boundary
2-3	$\geq 2$
4	$\geq 3$

2. If the recommendation is to assign the next patient to a dose level that already has 7 participants treated at the dose level, enrollment to the arm is stopped and the recommended dose level is declared the MTD.
3. Otherwise, the MTD is defined as the dose level that is recommended after the maximum sample size of 10 participants for the arm.

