### 10.4 Sample size and accrual

A maximum target accrual of 5 additional eligible participants is planned in Arm A (total accrual n=10) and 6 additional eligible participants in Arm C (total accrual n=10). A maximum target accrual of 26 additional eligible participants is planned in Arm B (total accrual n=30), but simulation results below indicate that the average estimated

sample size needed to complete accrual to Arm B is between 3.5 (total accrual n=7.5) and 11.3 (total accrual n=15.3) additional participants. Maximum total sample size for all arms is estimated to be approximately 23 additional participants (total accrual n=36). For estimation of ORR at the MTD, a sample size of 7 at the MTD produces a two-sided 80% binomial confidence interval with a width equal to 0.556 when the sample proportion is 0.5. Additional subjects will be enrolled to replace any subjects who are enrolled, but do not receive treatment. Accrual is estimated at 2 participants per month. Adjusting for an approximate 5% drop-out/ineligibility rate, maximum target accrual should not exceed 38 participants.

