### Arm B

Simulations were run to display the performance of the design characteristics in Arm B using the R statistical programming language. For each scenario, 5000 simulated trials were run using a random seed of 322348. The confidence level used to define the safety stopping guidelines was 80%. Simulation results include the true DLT probability at each combination, the percentage of trials in which each combination was recommended as the MTD, the average number of participants treated at each combination, the average sample size, and the percentage of trials stopped early for safety. The results displayed in the following tables were based upon a maximum target accrual of 30 participants where accrual was stopped when 7 participants were treated on the recommended combination.

Operating characteristics summary for proposed design over five scenarios					
	Scenario 1	Scenario 2	Scenario 3	Scenario 4	Scenario 5
Observed % DLTs	20.25%	21.38%	17.38%	27.27%	31.59%
Average sample size	8.42	8.84	7.51	12.44	15.32
MTD selection % ±5% of target*	92.50%	90.38%	98.70%	22.34%	37.28%
Avg # of pts treated ±5% of target*	6.93	6.91	6.99	2.8	4.4
% of early stopping for safety	0.00%	0.02%	0.00%	0.52%	1.84%

\* Includes combination with highest DLT rate if true DLT probability for all combinations is below 5% of the target

Operating Characteristics						
	True DLT probabilities		MTD Selection Percentage		Average Number of Patients Treated	
Scenario 1						
20mg/m  1,8,15	0.15	0.20	1.36	92.50	0.25	6.93
20mg/m  1,15	0.09	0.14	0.22	5.60	0.08	1.00
15mg/m  1,15	0.07	0.07	0.06	0.26	0.02	0.15
Scenario 2						
20mg/m  1,8,15	0.14	0.25	1.94	90.38	0.33	6.91
20mg/m  1,15	0.10	0.14	0.26	6.64	0.10	1.28
15mg/m  1,15	0.09	0.10	0.04	0.72	0.03	0.20
Scenario 3						
20mg/m  1,8,15	0.08	0.10	0.30	98.70	0.09	6.99
20mg/m  1,15	0.06	0.07	0.00	0.98	0.01	0.39
15mg/m  1,15	0.05	0.05	0.00	0.02	0.00	0.03
Scenario 4						
20mg/m  1,8,15	0.40	0.47	5.00	57.16	0.87	6.52
20mg/m  1,15	0.18	0.25	6.38	22.34	0.89	2.77
15mg/m  1,15	0.15	0.18	1.62	6.98	0.32	1.07
Scenario 5						
20mg/m  1,8,15	0.47	0.55	6.12	34.72	1.25	6.09
20mg/m  1,15	0.25	0.47	18.38	13.10	2.09	2.53
15mg/m  1,15	0.15	0.25	6.94	18.90	1.06	2.31

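### The Arm A operating characteristics in 10.5 omit the stop-at-7 rule of 10.3; with it, a level with a true 40% DLT rate is declared MTD in 78% of trials, not the printed 44.7%

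*Protocol*

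**What the plan says.** Protocol 10.3, Arms A and C, rule 2 says what happens when the model would "assign the next patient to a dose level that already has 7 participants treated at the dose level, enrollment to the arm is stopped": the recommended level is then declared the MTD. Rule 3 takes the level recommended after 10 participants only if that has not happened.

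Protocol 10.5 introduces the Arm A and Arm C simulations with "The results displayed in the following tables were based upon a maximum target accrual of 10 subjects". The table captions give 10 in total for each scenario, previous participants included. The Arm A table prints averages of 9.3, 8.7 and 8.0 participants on dose level 3. That is the level called Level 1 (start) in 10.1.

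The Arm B simulations in the same section are described differently: "where accrual was stopped when 7 participants were treated on the recommended combination". Section 10.4 also plans around 7: "a sample size of 7 at the MTD produces a two-sided 80% binomial confidence interval".

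**The concern.** Under rule 2 no level can hold more than 7 participants, so an average of 8.0 to 9.3 on one level cannot come from the design in 10.3. The Arm A table looks like a fixed design of 10.

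Determining the MTD is a primary objective, and 10.5 is the protocol's evidence of how well Arm A does so. Arm A starts with 5 of the 7 places on dose level 3 already used. The rule therefore tends to lock that level in before the model has seen enough data to move away from it. If the rule was left out, the table overstates how often a too-toxic top level would be rejected.

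**Working it through.** **Inputs.** From 10.2: skeleton 0.08, 0.15, 0.25; one-parameter power model fitted by maximum likelihood; next participant at the level whose estimate is closest to 25%; cohorts of 1; no skipping; no escalation after a DLT and no de-escalation after a non-DLT. From 10.3: the safety bound at the lowest level (at least 2 DLTs in 2 to 3, at least 3 in 4) and rule 2. From 10.1 and 10.5: 1 DLT in 5 on dose level 3, next participant on the same level, maximum 10. The true DLT rates are those of the three printed scenarios. All DLT paths were enumerated exactly, so there is no simulation error. The safety bound was checked before each further enrolment.

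**Step 1: reproduce the printed table, without rule 2.**

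| Scenario (true rates) | Selection of levels 1/2/3, computed | Printed | Average n on level 3, computed | Printed | Safety stops, computed | Printed |
|---|---|---|---|---|---|---|
| 1 (0.05/0.15/0.25) | 5.3/22.5/72.2% | 5.7/22.6/71.7% | 9.33 | 9.3 | 0.01% | 0.0% |
| 2 (0.15/0.25/0.40) | 18.5/35.9/45.4% | 18.9/36.2/44.7% | 8.68 | 8.7 | 0.22% | 0.24% |
| 3 (0.25/0.40/0.55) | 41.7/34.8/22.1% | 41.2/34.0/23.5% | 7.95 | 8.0 | 1.38% | 1.24% |

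The largest gap in selection is 1.4 percentage points (Scenario 3, level 3). The printed table is the design without rule 2.

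**Step 2: apply rule 2.**

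| Scenario | Selection of levels 1/2/3 | Average n on level 3 | Mean total N | Closed at exactly 7 | All 10 enrolled |
|---|---|---|---|---|---|
| 1 | 2.3/6.7/90.9% | 6.96 | 7.43 | 75% | 9.1% |
| 2 | 9.6/12.2/78.0% | 6.90 | 7.84 | 60% | 21.8% |
| 3 | 24.8/14.0/59.85% | 6.78 | 8.34 | 45% | 38.8% |

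Safety stops are unchanged at 0.01%, 0.22% and 1.38%.

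**Step 3: check the level 3 figure by hand.** Write p2 and p3 for the true rates on levels 2 and 3. Only two routes end with level 3 declared the MTD.

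- Participant 6 has no DLT, probability 1 − p3. Level 3 stands at 1/6 and stays recommended. Participant 7 brings it to 1/7 or 2/7. The level 3 estimate is then 0.143 or 0.286 and the level 2 estimate 0.070 or 0.180, so level 3 is closer to 0.25 both times. It now holds 7, and the arm closes.
- Participant 6 has a DLT (2/6 on level 3; estimates 0.222 on level 2 and 0.333 on level 3, so level 2 is next). Participant 7 has no DLT on level 2 (level 3 estimate 0.296, recommended again). Participant 8 has no DLT on level 3 (2/7; estimate 0.259). The arm closes. Probability p3(1 − p2)(1 − p3).

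The sum is (1 − p3) + p3(1 − p2)(1 − p3):

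- Scenario 1: 0.75 + 0.25 × 0.85 × 0.75 = 0.909
- Scenario 2: 0.60 + 0.40 × 0.75 × 0.60 = 0.780
- Scenario 3: 0.45 + 0.55 × 0.60 × 0.45 = 0.5985

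Mean N in Scenario 2 is about 7 × 0.60 + 8 × 0.18 + 10 × 0.22 = 7.84.

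**Step 4: sensitivity.** Dropping coherence or the no-skipping rule leaves level 3 selection unchanged. Checking the safety bound after the 10th participant as well changes only level 1, to 9.2% in Scenario 2 and 22.8% in Scenario 3.

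**Step 5: Arm C.** The Arm C table omits rule 2 as well, with averages of 8.5 and 7.5 on dose level 3 in Scenarios 1 and 2. Its starting data also conflict with 10.1, which has "Based upon the accumulated data from the previous 4 subjects (2 observed DLTs) accrued to Arm C" where the table caption has "Previously, there were 4 participants accrued (1 observed DLT) on dose level 3". From the caption's 1 in 4, level 3 selection in Scenario 2 is 33.3% without rule 2 (printed 32.2%) and 52.9% with it. From 2 in 4 with entry at Level -1, as 10.1 states, level 3 is selected in 29.4%, 11.4% and 2.6% and mean N is 10.0, 9.95 and 9.79, with or without rule 2. In Arm C the starting data are the larger fault.

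**The case against.** **Earlier participants might not count toward the 7.** This reading would rescue the table, but it fails. Section 10.4 leaves 5 further places in Arm A and 6 in Arm C, so rule 2 could never act. Rule 1 in 10.3 counts earlier participants ("given the accrual of previous participants to dose level 1 in Arms A and C, at most 4 participants can be accrued"). The Arm B simulations count the earlier 4: in Scenario 3 Combination 8 averages 6.99 with an average total of 7.51.

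**The basis is disclosed and the arithmetic is sound for a fixed 10.** This is true as far as it goes, and the fault is best called a mismatch between simulation and design. But in 10.3 the 10 is a maximum, and the Arm A and C text nowhere says that rule 2 was left out.

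**Rule 2 might not be applied mechanically.** The lead-in to the list in 10.3 speaks of a halt and a review, and 10.6 calls the safety bounds non-binding. The figures above do assume automatic application. Rule 2 itself is definite, however, and it defines the MTD; the non-binding remark concerns the DLT bounds.

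**Arm A has probably closed.** Arm B opens only after Arms A and C finish enrolling, and 10.1 reports 4 participants already on Arm B. Sections 10.1 and 10.4 still describe further Arm A accrual, so closure is an inference. If it is right, a corrected table alters no allocation, and the observed DLT counts carry most of the information. The error properties of the declared MTD would still have to be read from the correct table.

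**Scenario 2 alone is one-sided.** This is a fair point: rule 2 improves correct selection in Scenario 1. Also, a lower level is still chosen in 21.8% of trials in Scenario 2 and 38.8% in Scenario 3.

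**Conclusion.** The concern holds. The Arm A figures in 10.5 belong to a fixed design of 10, not to the design in 10.3. Under rule 2 a level with a true 40% DLT rate is declared MTD in 78.0% of trials instead of 44.7%, and one with a true 55% rate in 59.85% instead of 23.5%. The true MTD is selected in 12.2% instead of 36.2% (Scenario 2), 24.8% instead of 41.2% (Scenario 3) and 90.9% instead of 71.7% (Scenario 1).

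This rests on the CRM as written in 10.2, the start at 1 DLT in 5, earlier participants counting toward the 7, and rule 2 being applied as worded. Because the rule that defines the MTD and its published performance describe different designs, the table must be corrected.

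**What to change.** Reconcile 10.3 with 10.5:

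- **Arm A:** re-run the simulations with rule 2 applied and reprint selection percentages, averages per level, mean total sample size and safety stops.
- **Arm C:** first settle the starting data against 10.1, then re-run with rule 2 applied and reprint.
- **Text of 10.5:** state that rule 2 was applied, as the Arm B text already does.
- **Alternative:** if the sponsor intends the fixed design of 10 that was simulated, 10.3 must say that rule 2 does not apply to Arms A and C.

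The cost is one short simulation run and two reprinted tables. If rule 2 stays as written, enrolment and participant numbers do not change.
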